#### **11.1.3. Hybrid ACR Response**

The hybrid ACR is an outcome measure that combines the ACR20, the ACR50, and the ACR70 and a continuous score of the mean improvement in core set measures (Number of tender joints, Number of swollen joints, Pain (VAS), Disease activity (VAS), HAQ, CRP or ESR). Note that CRP will be used for the hybrid ACR score derivation, unless it is missing, in which case ESR will be used.

The steps to calculate the hybrid ACR score are as follows:

- (1) For each core set measure, the post-baseline score is subtracted from the baseline score, and the percentage change in each measure determined.
- (2) If a core set measure worsened by more than 100%, that percentage change is set to -100%.
- (3) The percentage change for all core set measures is averaged to give the mean % change in core set measures.
- (4) The hybrid ACR score is determined from the following table. The ACR20, ACR50, or ACR70 status of the patient (left column) is taken, along with the mean percentage change in core set items calculated in step (3); the hybrid ACR score is where they intersect in the table.

**Table 5: Scoring Method for Hybrid ACR**

Patient ACR Status	Mean % change in core set measures			
	<20	≥20, <50	≥50, <70	≥70
Not ACR20	Mean % change in core set measures	19.99	19.99	19.99
ACR20 but not ACR50	20	Mean % change in core set measures	49.99	49.99
ACR50 but not ACR70	50	50	Mean % change in core set measures	69.99
ACR70	70	70	70	Mean % change in core set measures

Source: American College of Rheumatology Committee to Reevaluate Improvement Criteria 2007.

Descriptive statistics of the hybrid ACR score will be presented by treatment group at each visit for the efficacy population, efficacy – end treatment course in Main Study Period subset and efficacy – Extension Study Period subset. A listing will also be provided for the all-randomized population, by treatment group, showing the hybrid ACR score, ACR responder status, and the mean % change in core set measures. Hybrid ACR score will be presented to two decimal places.

### 11.2. DAS28

The ANCOVA comparing the change from baseline of DAS28(CRP) and DAS28(ESR) at 24 weeks of treatment between two treatment groups, CT-P10 and combined Rituxan and MabThera group will be analyzed, considering the treatment as a fixed effect and gender, country, race, study part, interaction of treatment group with study part, prior anti-TNF- $\alpha$  blocker status (intolerance case versus inadequate response), and RF or anti-CCP status (both positive versus both negative versus either RF or anti-CCP negative) fitted as covariates. Clinically relevant variables at baseline are used as the covariates for adjusted means. If country is found to be unsuitable as a covariate due to the number of levels, then region (EU, non-EU), which may pool countries based on continents, may be used instead. Additional ANCOVA will be conducted in patients whose ADA status result at Week 24 is “Negative”.

The least squares mean and corresponding standard error of the change from baseline in DAS28 at Week 24 will be presented for each treatment group. Point estimates (least squares mean and difference of least squares means), 90% confidence interval (CI) for the treatment difference and p-value with an interaction effect between study part and treatment group will also be provided. When there are Significant GCP non-compliance sites, an additional sensitivity analysis will be performed.

All-randomized population and efficacy population will be used for analysis of change from baseline of DAS28 (ANCOVA), respectively.

Descriptive statistics for actual value and change from baseline in disease activity measured by DAS28 (CRP) and DAS28 (ESR) will be summarized at each visit for the efficacy population, efficacy – 2nd treatment course in Main Study Period subset and efficacy – Extension Study Period subset by treatment group. Descriptive statistics for actual value and change from baseline in DAS28 (CRP) and DAS28 (ESR) in patients whose swollen joints (of 66 assessed) and tender joints (of 68 assessed) equal to or higher than 8 at baseline at each visit will be also summarized for the efficacy population, efficacy – 2nd treatment course in Main Study Period subset and efficacy – Extension Study Period subset. In addition, descriptive statistics of DAS28 at each visit will be summarized for the Efficacy (Antibody Negative/Positive Subset).

Data from the eCRF, DAS28 components, DAS28 value and change from baseline for both CRP and ESR will be listed by treatment group for the all-randomized population.

Disease activity score in 28 joints (DAS28) will be calculated in two ways using the following two equations [13]:

$$\text{DAS28 (ESR)} = (0.56 \times \sqrt{TJC28}) + (0.28 \times \sqrt{SJC28}) + (0.70 \times \ln(\text{ESR})) + (0.014 \times GH)$$

$$\text{DAS28 (CRP)} = (0.56 \times \sqrt{TJC28}) + (0.28 \times \sqrt{SJC28}) + (0.36 \times \ln(\text{CRP} + 1)) + (0.014 \times GH) + 0.96$$

Where:

TJC28 = number of tender joints (0-28): tender joint count (TJC)

SJC28 = number of swollen joints (0-28): swollen joint count (SJC)

ESR = ESR measurement (mm/h)

CRP = CRP measurement (mg/L)

GH = Patient Global Assessment of Disease Activity measured on VAS (0 – 100 mm)

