7.8.2 Efficacy Analyses

7.8.2.1 Primary Efficacy Analysis

The primary efficacy analysis includes patients from Part 1 and Part 2. The primary analysis for DAS28 is an analysis of covariance (ANCOVA) comparing the change from baseline of DAS28 after 24 weeks of treatment between two treatment groups, CT-P10 and reference products, considering the treatment as a fixed effect and country, gender, race, prior anti-TNF- α blocker status (inadequate response versus intolerant case), and RF or anti-CCP status (both positive versus both negative versus either RF or anti-CCP negative) fitted as covariates. If country is found to be unsuitable as a covariate due to the number of levels, then this may be pooled into a new variable, region defined in the SAP, for use as a covariate.

Similarity for the change from baseline of DAS28 (CRP) at week 24 will be evaluated based on the two-sided 90% confidence interval obtained from the ANCOVA model for the difference of means of the change in DAS28 (CRP) between the two treatment groups. The equivalence margin for the 90% CI is defined as [-0.50, 0.50].

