## 2. Introduction

Rheumatoid arthritis (RA) is a chronic systemic inflammatory disease that affects 0.8% to 1.0% of all populations. Rheumatoid arthritis primarily affects diarthrodial joints in a symmetrical distribution with an additive disease evolution over years (Scott et al 1987). The hallmark of the disease is damage and disruption of joint integrity, starting early in the course of RA. In most cases, bone erosions progress and lead to irreversible joint deformities. It is estimated that around one-third of patients have radiographic evidence of bone erosions at the time of diagnosis, and this increases to almost 60% 2 years after diagnosis (van der Heijde 1995). Unless the inflammatory processes are halted or controlled, the disease leads to substantial disability, comorbidities, and in some cases, premature death (Lard et al 2001).

CT-P10 is a monoclonal antibody, currently being developed by CELLTRION, Inc., which is intended to be formulated as a biosimilar candidate of Rituxan and MabThera, compounds with established efficacy in the treatment of active RA (MabThera 2015; Rituxan 2014). Rituximab is approved as Rituxan in the United States and as MabThera in other countries. CT-P10 can offer a more affordable treatment for RA than the originator protein if similar efficacy and safety are demonstrated and allow increased access to this valuable drug with a proven mechanism of action in RA patients. This is a similarity study that consists of 3 parallel arms: Rituxan (US-licensed), MabThera (EU-approved), and CT-P10. All statistical assessments will be direct comparisons between the treatment groups at specified time points.

This SAP covers all specified analysis and is based on the following documents:

- Protocol Version 5.1, including Country-Specific Protocol Amendment 1 (US) – 01 April 2016
- MSL Final Version 4.00 – 21 August 2015

According to the study protocol, the sponsor plans to prepare 2 Clinical Study Reports (CSRs). However, CSRs can be generated during the Study Period in addition to the 2 clinical study reports as planned for regulatory or academic purpose:

- To report data for each patient up to Week 24
- To report data after completion of study

This statistical analysis plan (SAP) defines the statistical methods and data presentations to be used by the CELLTRION biostatistics team for final analysis.

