### **5.3. Randomization, Stratification, and Blinding**

Patients will be randomly assigned to a treatment group on Day 0 (before administration of study drug) by using a computer-generated randomization schedule prepared before the study. The randomization will be stratified by country, prior anti-TNF- $\alpha$  blocker status (inadequate response versus intolerant case), and Rheumatoid Factor (RF) or Anti-Cyclic Citrullinated Peptide (anti-CCP) status (both positive versus both negative versus either RF or anti-CCP negative). Patients with positive status for either RF or anti-CCP at screening will be classified as a positive.

This study will be double-blind. The blind should be broken only if specific emergency treatment would be dictated by knowing the study drug status of the patient. In such cases, the investigator must contact the medical monitor. If the investigator is unable to contact the medical monitor, the investigator may, in an emergency, determine the identity of the study drug by using the applicable procedure in the interactive web response system (IWRS) or interactive voice response system (IVRS).

The overall randomization code will be broken only for reporting purposes. The reporting of the co-primary endpoints for PK in Part 1 and Efficacy in Part 2 at Week 24 will be reported concurrently. The unblinded statistical analyses will be performed by CELLTRION. Only relevant [REDACTED] Biostatistics, Medical Writing and the sponsor will be unblinded at this stage; all other study personnel will remain blinded until the end of the study. Final determination of the analysis sets will occur prior to finalizing the database for each analysis. In addition, the blind will be broken for reporting to the Data Safety Monitoring Board (DSMB).

The randomization code will not be revealed to study patients, parents or guardians, study center staff, or investigators.

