#### **5.5. Definition of Baseline**

The baseline value will be considered to be the last non-missing value before the first infusion. Post-baseline visits will be considered to be all visits after the first date of infusion.

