### **5.8. Missing Values and Outliers**

In order to evaluate the impact of missing data on the efficacy primary endpoint results, additional analyses with missing data imputation will be conducted for the primary efficacy endpoint of DAS28 (CRP) at Week 24 in all-randomized population.

Two imputation methods will be used for sensitivity analysis: Last observation carried forwards (LOCF) and Multiple imputation (MI) with the Missing at random (MAR) assumption. In addition, Tipping point analysis will be conducted based on MI results.

LOCF will impute missing values by the last value observed. MI with the MAR assumption will use regression method to impute missing data. Gender, country (or region), race, baseline value of DAS28 (CRP), prior anti-TNF alpha blocker status (intolerance case versus inadequate response), RF or anti-CCP status (both positive versus both negative versus either RF or anti-CCP negative), study part, treatment group and interaction of treatment group with study part will be used as regression covariates. 10 imputed datasets will be created by multiple imputations, and results from these 10 datasets will be pooled.

LOCF and MI with the MAR results will be provided displaying descriptive statistics for actual value and change from baseline in DAS28 (CRP) at Week 24. Additional, ANCOVA for the DAS 28 (CRP) will be conducted along with its 90% CI between CT-P10 and Reference products treatment group.

Tipping point analyses will be conducted under MNAR (Missing Not at Random) scenarios. Imputed values will be shifted gradually from the imputed values by MI, by treatment groups (CT-P10 versus combined Rituxan and MabThera group) to make MNAR scenarios. A point estimate and 90% confidence interval (CI) for the treatment difference will also be calculated using an analysis of covariance (ANCOVA) considering the treatment as a fixed effect and gender, country (or region), race, study part, interaction of treatment group with study part, prior anti-TNF- $\alpha$  blocker status (intolerance case versus inadequate response), and RF or anti-CCP status (both positive versus both negative versus either RF or anti-CCP negative) fitted as covariates under these scenarios, and the scenario under which confidence interval no longer

rules out differences in the change from baseline of DAS28 (CRP) at Week 24 for the therapeutic equivalence margin of  $\pm 0.5$  will be displayed.

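### The primary ANCOVA of change in DAS28 (CRP) omits baseline DAS28: the test is valid and adequately powered, but it gives up precision and leaves the estimate exposed to chance baseline imbalance

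*SAP*

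**What the plan says.** Protocol 7.8.2.1 defines the primary comparison as an ANCOVA of change in DAS28 at Week 24 "considering the treatment as a fixed effect and country, gender, race", with prior anti-TNF status and RF/anti-CCP status as further covariates. SAP 11.2 adds two terms for study part: "considering the treatment as a fixed effect and gender, country, race, study part, interaction of treatment group with study part". The tipping-point ANCOVA in SAP 5.8 repeats that list: "considering the treatment as a fixed effect and gender, country (or region), race, study part, interaction of treatment group with study part". None of the three contains baseline DAS28. The LOCF and multiple-imputation ANCOVAs in SAP 5.8 have no covariate list of their own.

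The variable is available:

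- DAS28 is assessed at Screening and before infusion on Day 0 (Protocol Table 4).
- SAP 5.5 defines baseline: "The baseline value will be considered to be the last non-missing value before the first infusion".
- The imputation regression in SAP 5.8 already uses it: "Gender, country (or region), race, baseline value of DAS28 (CRP), prior anti-TNF alpha blocker status".

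On the design side, "The randomization will be stratified by country", and also by prior anti-TNF status and RF/anti-CCP status. Disease activity is not a stratification factor (Protocol 5.1, SAP 5.3). No sensitivity analysis adjusted for baseline DAS28 is planned.

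**The concern.** Similarity is concluded if the 90% CI for the treatment difference lies within ±0.50. Subtracting baseline to form a change score does not generally remove the dependence on baseline, and whatever correlation is left between baseline and change stays in the residual.

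This has two consequences. The CI is wider than it needs to be whenever that correlation is not zero. And if the arms happen to differ at baseline, part of the gap passes into the treatment difference. Averaged over randomisations this cancels, but in the single realised trial it does not. In an equivalence trial such a shift can cause a false failure or mask a real difference. A reader would have to judge it informally from the descriptive tables, although one model term would deal with it.

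Using baseline DAS28 in the imputation model shows that it is available. It is not in itself an inconsistency.

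**Working it through.** **Inputs**

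- Margin ±0.50 and two-sided 90% CI, i.e. two one-sided tests at 0.05 (Protocol 7.8.2.1).
- SD of change 1.32; 133 CT-P10 and 189 reference evaluable; stated power about 90% (Protocol 7.5, SAP 5.2).
- 56 evaluable per arm from Part 1 (Protocol Synopsis). Part 1 is therefore 56 v 2 × 56 = 112, and Part 2 is 133 − 56 = 77 v 189 − 112 = 77.
- Assumed, because not in the documents: r (absolute value) from 0.1 to 0.5; true difference 0 or 0.1; 1.32 taken as the residual SD before baseline is added; equal weighting of the two parts when the interaction is fitted.

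**The plan's own figure**

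SE = 1.32 × √(1/133 + 1/189) = 1.32 × 0.1132 = 0.149.

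Normal approximation at a true difference of 0: power = 2Φ(0.50/0.1494 − 1.645) − 1 = 91.1%. Integrating over the distribution of the residual variance (320 df) gives 91.0%. The stated figure of about 90% is reproduced.

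With the treatment-by-part interaction, the SE factor is √[0.25 × (1/56 + 1/112 + 1/77 + 1/77)] = 0.1148, so SE = 0.152. Power on 318 df is 90.0%.

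Simulation of the model without baseline, at a true difference of 0.50, gave a type I error of 4.8% to 4.9% for r = 0, 0.3 and 0.5. The test is valid as it stands.

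**Adding baseline**

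Residual SD = 1.32 × √(1 − r²), with 1 df fewer. Half-width = t(0.95) × SD × 0.1132, so the unadjusted value is 1.6496 × 0.1494 = 0.246.

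| r | Residual SD | 90% CI half-width | Power, diff 0 | Power, diff 0, interaction | Power, diff 0.1 | Power, diff 0.1, interaction |
|---|---|---|---|---|---|---|
| no baseline term | 1.320 | 0.246 | 91.0% | 90.0% | 83.9% | 82.8% |
| 0.1 | 1.313 | 0.245 | 91.3% | 90.4% | 84.2% | 83.2% |
| 0.2 | 1.293 | 0.241 | 92.2% | 91.4% | 85.3% | 84.3% |
| 0.3 | 1.259 | 0.235 | 93.7% | 92.9% | 87.1% | 86.1% |
| 0.4 | 1.210 | 0.226 | 95.4% | 94.8% | 89.5% | 88.6% |
| 0.5 | 1.143 | 0.213 | 97.3% | 96.9% | 92.4% | 91.7% |

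The CI narrows by 1 − √(1 − r²), from 0.5% at r = 0.1 to 13.4% at r = 0.5. At r of 0.2 or less the power gain is about 1.5 points at most.

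**Shift from a chance baseline gap**

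The slope of change on baseline is r × 1.32 / SD(baseline). A gap of k standard errors is k × SD(baseline) × 0.1132. Their product is k × r × 0.149, and the baseline SD cancels.

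- k = 1 (exceeded in about 32% of trials): 0.015 at r = 0.1, 0.075 at r = 0.5.
- k = 2 (exceeded in about 5%): 0.030 at r = 0.1, 0.149 at r = 0.5.

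On the absolute scale, a gap of 0.2 DAS28 units or more has a probability of 1.2% if the baseline SD is 0.7 and 7.7% if it is 1.0 (both SDs assumed).

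**The case against.** The strongest reply is that nothing is broken. The test is unbiased over randomisation, the CI holds its error rate and the power target is met. All of that is correct, and it limits the point to an improvement.

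The size of the gain rests on an r that the documents do not give. At r = 0 nothing is gained and at r = 0.1 almost nothing. This also stands: the omission is certain, its cost is not.

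The 1.32 is stated as the SD of the change, not as a residual SD after country, gender, race and serostatus. If those covariates explained, say, 10% of the variance (an assumption), power without baseline would already be 93.9%, rising to 94.9% at r = 0.2 and 95.9% at r = 0.3. The power gains in the table would then be smaller. The percentage narrowing of the CI for a given r would not change.

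The conditional shift is modest. Reaching 0.149 needs both a 2-SE gap and the top of the assumed range, and the direction may be either way. Baseline DAS28 will also be tabulated by treatment, so a large gap would be seen. But a table only shows the gap and does not correct the estimate for it.

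The sponsor might point to the remark in SAP 11.2 that clinically relevant baseline variables serve as covariates. It does not bring baseline DAS28 in. The same remark appears in SAP 12.2, where baseline values are listed separately in the model, so it describes the listed covariates and adds none. That pharmacodynamic model also shows that the plan adjusts for baseline elsewhere.

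Finally, the primary model may no longer be open to change. At the Week 24 report, "Biostatistics, Medical Writing and the sponsor will be unblinded at this stage", and SAP section 2 says the document sets out methods and "data presentations to be used by the CELLTRION biostatistics team for final analysis". The documents do not settle whether unblinding has already happened, and the fix has to allow for both cases.

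**Conclusion.** The concern holds, as a recommended improvement and not as the correction of an error. Baseline DAS28 is absent from every covariate list named for the primary endpoint, although it costs nothing to include.

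For r between 0.1 and 0.5, the omission forgoes 0.3 to 6.3 power points at a true difference of 0 and 0.3 to 8.5 points at a true difference of 0.1 (without the interaction term). It also leaves the realised difference open to a shift of up to about 0.15 in an unfavourable but not extreme case.

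These figures assume that 1.32 is the residual SD before baseline is added and that the evaluable numbers are as planned. The sample size needs no change, and the validity of the planned test is not in question.

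**What to change.** Establish first whether any Week 24 treatment-level data have been unblinded to the sponsor (Protocol 5.5.1, SAP 5.3).

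- **If still blinded:** add baseline DAS28 (CRP) as a continuous covariate to the primary ANCOVA (Protocol 7.8.2.1, SAP 11.2) and to the LOCF, multiple-imputation and tipping-point ANCOVAs (SAP 5.8). State the covariates of the LOCF and imputation models explicitly. Use baseline DAS28 (ESR) in the DAS28 (ESR) model. Keep the present model as a sensitivity analysis.
- **If already unblinded:** keep the present model as primary and report the baseline-adjusted model as a clearly labelled sensitivity analysis, so that a reader can see whether the similarity conclusion depends on a baseline gap.

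The cost is one covariate and one degree of freedom, with no new data. Changing the primary model is safe only before the Week 24 unblinding.

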### 11.3. EULAR Response Criteria

The European League Against Rheumatism Response (EULAR) response criteria [3] categorizes the DAS28 response (i.e., good, moderate, or none) based on changes in DAS28 from baseline.

**Table 6: European League Against Rheumatism Response Criteria**

Present DAS28	DAS28 Improvement from Baseline		
	>1.2	>0.6 and ≤1.2	≤0.6
≤3.2	Good response	Moderate response	No response
>3.2 and ≤5.1	Moderate response	Moderate response	No response
>5.1	Moderate response	No response	No response

Frequencies and percentages of EULAR response categories (based on both DAS28 (ESR) and DAS28 (CRP)) will be summarized by treatment group for the efficacy population, efficacy – 2nd treatment course in Main Study Period subset and efficacy – Extension Study Period subset at each visit.

EULAR response categories, corresponding DAS28 actual values and DAS28 change from baseline for both ESR and CRP, along with DAS28 components, will be listed by treatment group for the all-randomized population.

#### 11.4. Clinical Disease Activity Index and Simplified Disease Active Index

Clinical Disease Activity Index (CDAI) and Simplified Disease Activity Index (SDAI) are calculated at each visit as follows:

**Table 7: Clinical Disease Activity Index and Simplified Disease Activity Index Formulas**

Index	Formula
CDAI	SJC28 + TJC28 + PGA + EGA
SDAI	SJC28 + TJC28 + PGA + EGA + CRP

SJC28 = swollen joint count (0-28); TJC28 = tender joint count (0-28)

PGA = patient global assessment of disease activity (0-10 cm)

EGA = evaluator/physician global assessment of disease activity (0-10 cm)

CRP = C-reactive protein (mg/dL)

Note: Prior to calculation of the CDAI and SDAI, the Patient Global Assessment of Disease Activity and Physician Global Assessment of Disease Activity VAS results should be converted from mm to cm [1].

Descriptive statistics for actual value and change from baseline of CDAI and SDAI will be presented by treatment group for the efficacy population, efficacy – 2nd treatment course in Main Study Period subset and efficacy – Extension Study Period subset at each visit. In addition, a listing will be provided by treatment group for the all-randomized population showing the CDAI and SDAI values.

